6.7. Study Drug Materials and Management

TAS3351 will be supplied by the Sponsor.

Detailed information such as the requirements for accountability and disposal of study drug can be found in the Pharmacy Manual, which will be provided separately.

6.7.1. Description of Study Drug

A description of the study drug and the recommended storage condition are provided in [Table 11](#).

Table 11: Description of TAS3351

Generic name	Not assigned
Dosage form	25, 100, and 200 mg tablets
Appearance	Pale yellow to grey solid
Formulation	TAS3351 tablets (25, 100, and 200 mg) contain 25, 100, and 200 mg of TAS3351 drug substance free base, respectively. In addition, these tablets contain the following inactive ingredients: Microcrystalline cellulose Lactose monohydrate Croscarmellose sodium Hydroxypropyl methyl cellulose Colloidal silicone dioxide Sodium stearyl fumarate Magnesium stearate HPCM-based color coating
Storage condition	Store TAS3351 tablets according to the label.

6.7.2. Packaging and Labeling

TAS3351 will be packaged and labeled according to local laws and regulations.

6.7.3. Accountability

The Investigator is responsible for ensuring that all study drug received at the site is inventoried and accounted for throughout the study. All study drugs will be stored and disposed of according to the Sponsor's instructions. The dispensing of study drug to the patient and the return of study drug from the patient must be documented. Patients must be instructed to return all original containers, whether they are empty or still containing the study drug.

Refer to the Pharmacy Manual for more details.

7. STUDY ASSESSMENTS

7.1. Study Assessments and Procedures

The Schedule of Events (Section 1.3) summarizes the frequency and timing of all study assessments applicable to this study.

Descriptions of the study assessments required are presented in Table 12.

Table 12: Study Assessments

Assessment	Details
General Study Assessments	
Written informed consent/consent for study continuation	Date when written informed consent was obtained.
Review of inclusion/exclusion criteria	Eligibility must be assessed during the screening period and should be confirmed prior to the first dose of study drug as clinically indicated. See Sections 5.1 and 5.2.
Demographics/medical history	Sex, age, race/ethnicity, clinical diagnosis, date of diagnosis, method of diagnosis, prior cancer therapy, and relevant medical history (past and concurrent).
Baseline signs and symptoms	Signs and symptoms which occurred after signing of ICF but before administration of first dose of TAS3351.
Concomitant medication/concomitant therapy	Medication/therapy with period and the reason of concomitant use (including blood and blood products). Include all medications/therapies administered from the time ICF is signed through 30 days after administration of the last dose of TAS3351 or until the start of new anticancer therapy.
Compliance	Drug accountability of investigational drug. See Section 6.3 and Section 6.7.3.
Safety	
Physical examination	Physical examinations at screening include assessments of general appearance, skin, head and neck (including ears, eyes, nose and throat), respiratory, cardiovascular, abdomen, lymph nodes, thyroid, musculoskeletal (including spine and extremities), and neurological systems. Targeted symptom directed physical examinations may be utilized on the basis of clinical observations at subsequent visits. Examination of skin should be performed at each timepoint indicated in the Schedule of Events.
AE monitoring	See Section 10.
Local and central ECGs	Resting, semi-recumbent 12-lead ECGs; triplicates at baseline, Cycles 1-3, and as clinically indicated (eg, for QT prolongation, see dose modifications in Section 6.2.1.2); RR interval (heart rate), QT interval, QTcF interval and abnormal finding by 12-lead ECG. See Section 7.1.2.

Assessment	Details
Vital signs, height and body weight	Systolic and diastolic blood pressure, pulse rate, body temperature, height (for body mass index calculations, recorded at baseline only) and body weight.
Echocardiography/MUGA	Baseline echocardiography/MUGA (multi-gated acquisition scan) is required. Left ventricular ejection fraction (LVEF) monitoring is needed every 4 cycles during TAS3351 treatment, and as clinically indicated. LVEF can be assessed by ECHO or MUGA; same modality should be used for a patient at screening and after dosing. See Section 7.1.3.
Hematology	Red blood cell (RBC) count, hemoglobin, hematocrit, platelets, white blood cell (WBC) count with differential: neutrophils (ANC), lymphocytes, monocytes, eosinophils, basophils. See Section 7.1.4.
Serum chemistry	AST, ALT, ALP, total bilirubin, direct bilirubin, albumin, LDH, triglyceride, total cholesterol, creatinine, BUN, Na, K, Cl, Ca (corrected value), Mg, blood glucose, C reactive protein (CRP), lipase, amylase, creatinine clearance (if there is a measured value, use the measured value) or eGFR. See Section 7.1.4. For a calculated CrCl value, use the Cockcroft-Gault formula: Male: $\text{CrCl} = \frac{(140 - [\text{insert age in years}] \times [\text{insert weight in kg}])}{72 \times [\text{insert serum creatinine in mg/dL}]}$ Female: $\text{CrCl} = \frac{(140 - [\text{insert age in years}] \times [\text{insert weight in kg}])}{72 \times [\text{insert serum creatinine in mg/dL}]} \times 0.85$
Coagulation	PT-INR, APTT, and fibrinogen. See Section 7.1.4 .
Urinalysis	Urine protein (qualitative), sediment, occult blood by dipstick or laboratory. If urine protein is 2+, add urinary β 2-microglobulin and quantitative measurement of proteinuria (24-hour urine collection for protein preferred). See Section 7.1.4.
Pregnancy test	For all female patients of childbearing potential: Serum or urine human chorionic gonadotrophin (human chorionic stimulating hormone) test (see the local regulation and/or CTFG recommendations). For screening, serum test required.
ECOG performance status	See Oken et al. for details. ²⁷
Efficacy and other	
Efficacy assessments	Efficacy assessment by tumor imaging. See Section 7.1.1.
Survival follow-up	Patient or family should be contacted for survival follow-up until withdrawal of consent, death, or loss to follow-up, until study completion. This should also include further anti-cancer treatments administered.
PK blood sampling	See Section 8.1 and Laboratory Manual.
Pharmacodynamic biomarker sampling	See Section 11.

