5.1. Inclusion Criteria

A patient must meet all of the following inclusion criteria to be eligible for participation in this study:

1. Provide written informed consent
2. ≥ 18 years of age (or meets the country's regulatory definition for legal adult age, whichever is greater)
3. Histologically or cytologically confirmed, locally advanced, non-resectable or metastatic NSCLC
4. Has received the following prior treatment and no more than 2 lines of prior cytotoxic chemotherapy for locally advanced or metastatic disease setting:
 - a. **Part A1** (Phase 1 Dose Escalation): Standard of care (SOC) that is available to the patient, unless contraindicated, or intolerable to the patient
 - b. **Part A2**: Progression on third-generation EGFR TKI (eg, osimertinib, lazertinib)
 - c. **Parts B and C**: Progression on third-generation EGFR TKI (eg, osimertinib, lazertinib)
5. Has the following *EGFR*mt status as determined by a CLIA certified (US), locally certified (outside of the US), or the study central laboratory based on tumor tissue or plasma cfDNA:
 - a. **Part A1** (Phase 1 Dose Escalation): Any *EGFR*mt
 - b. **Parts A2, B, and C**: Any sensitizing *EGFR*mt and a confirmed C797S *EGFR*mt (Note: no T790M *EGFR*mt required)
6. Has tumor tissue available collected after progression on the most recent systemic EGFR TKI treatment in a quantity sufficient to allow for analysis of *EGFR*mt status by the Sponsor's central laboratory (optional for **Part A1 only**). Please refer to the Laboratory Manual for details.
7. Has measurable disease per RECIST v1.1 (optional for patients in Part A1)
8. Eastern Cooperative Oncology Group (ECOG) performance status 0 or 1
9. Adequate organ function as defined by the following criteria:
 - a. Absolute neutrophil count (ANC) $\geq 1.5 \times 10^9/L$
 - b. Platelet count $\geq 100,000/mm^3$ ($\geq 100 \times 10^9/L$); last transfusion of blood products must be ≥ 2 weeks prior to start of study treatment.
 - c. Hemoglobin ≥ 9.0 g/dL
 - d. Alanine aminotransferase (ALT) and aspartate aminotransferase (AST) $\leq 3.0 \times$ upper limit of normal (ULN); if liver function abnormalities are due to underlying liver metastasis, AST and ALT $\leq 5.0 \times$ ULN
 - e. Total bilirubin $\leq 1.5 \times$ ULN, or $\leq 3.0 \times$ ULN for patients with Gilbert's syndrome
 - f. Creatinine clearance (CrCl) (calculated or measured value): ≥ 50 mL/min. For calculated CrCl, use the Cockcroft-Gault formula

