6.1.2. Dose-limiting Toxicity

Dose-limiting toxicity (DLT) will be assessed during the first cycle (including the PK lead-in period for patients in Part A1). The occurrence of any toxicity outlined in [Table 7](#) that is clinically significant will be considered a DLT, excluding toxicities clearly related to disease progression or intercurrent illness. The investigator must report all DLTs to the Sponsor promptly during the dose escalation part and well in advance of the dose escalation call. In addition, meetings between the Sponsor and investigators will be held on a regular basis to review safety data and in the event of emerging safety issues.

Table 7: Definition of Dose Limiting Toxicity

Toxicity	DLT Definition
Hematologic	
 • Grade 4 neutropenia lasting >7 consecutive days • Grade 4 thrombocytopenia • Grade 3 thrombocytopenia associated with clinically significant bleeding requiring intervention • Febrile neutropenia (ANC <1000/mm³ with a single body temperature of >38.3°C [101 °F] or a sustained temperature of ≥38°C [100.4°F] for more than 1 hour)
Hepatic	
 • Grade ≥3 total bilirubin elevation • Grade ≥3 AST and/or ALT elevation • For patients with liver metastases, AST or ALT >8 × ULN regardless of duration or AST or ALT >5 × ULN but ≤8 × ULN lasting ≥7 consecutive days
	
 • Hy's Law criteria concurrent observation of the following, with no other reason found to explain the findings (such as viral hepatitis A, B, or C; pre-existing or acute liver disease; or another drug capable of causing the observed liver injury): 
 – Elevated aminotransferase enzymes >3 × ULN – Associated with an increase in bilirubin >2 × ULN – Absence of initial findings of cholestasis (elevated ALP)
Renal	
 • Calculated CrCl <30 mL/min for >3 days despite optimal supportive care
Skin	
 • Grade ≥3 skin toxicity uncontrolled by adequate skin therapy, including topical steroid and/or systemic corticosteroid therapy that does not return to Grade ≤2 within 7 days

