Urinalysis	Qualitative: Urine protein, sediment, occult blood by dipstick or laboratory. Quantitative: If urine protein is 2+ to 4+, add urinary β 2-microglobulin and proteinuria.

For a calculated creatinine clearance (CrCl) value, use the Cockcroft-Gault formula:

Male CrCl (mL/min) = $\text{weight (kg)} \times (140 - \text{age (years)}) / [72 \times \text{serum creatinine (mg/dL)}]$

Female CrCl (mL/min) = male CrCl \times 0.85

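### Protocol Table 12 misplaces the Cockcroft-Gault bracket, and one renal laboratory item can mix measured CrCl, calculated CrCl and eGFR in the SAP's change and shift tables

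*Protocol*

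**What the plan says.** **Formula.** The serum chemistry row of protocol Table 12 (Section 7.1) introduces its equations with "For a calculated CrCl value, use the Cockcroft-Gault formula: Male". In both the male and the female equation the bracket opens before 140 and closes after weight, not after age. SAP Section 5.6.4 prints the equations in its Table 8 and again below it, under "For a calculated creatinine clearance (CrCl) value, use the Cockcroft-Gault formula". Both times the bracket closes after age.

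**Where calculated CrCl is used.** Inclusion criterion 9f (protocol Section 5.1) requires at least 50 mL/min, calculated or measured, and adds "For calculated CrCl, use the Cockcroft-Gault formula". The renal DLT in protocol Table 7 (Section 6.1.2) is "Calculated CrCl <30 mL/min for >3 days despite optimal supportive care".

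**Renal item.** Table 12 lists "creatinine clearance (if there is a measured value, use the measured value) or eGFR. See Section 7.1.4". SAP Table 8 repeats the item. SAP 5.6.4 then summarizes laboratory results by parameter, with change from baseline at each visit and shifts from baseline grade to worst grade.

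**Proteinuria.** The protocol's trigger for the additional urine tests is "If urine protein is 2+, add urinary". The SAP's is "If urine protein is 2+ to 4+, add urinary".

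**The concern.** Table 12 is the only place in the protocol where the equation is written out, and calculated CrCl serves both an entry criterion and a DLT criterion. A formula that cannot return a valid value should not stand there. The SAP does not make good the gap for the whole trial: by its Section 1 it covers Parts A and B only, so the 100 planned Part C patients have no correctly printed version in these documents.

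The renal item is a separate matter. If a patient has one method at baseline and another later, the tabulated change contains a method difference that has nothing to do with the drug. Laboratory work is local, and outside laboratories are allowed (protocol Section 10.2), so a change of method is realistic.

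**Working it through.** **1. The bracket.** The inputs are the two printed forms and the minimum age of 18 (criterion 2). The other ages, the weights and the creatinine values are assumed examples.

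- Protocol form: (140 − age × weight) / (72 × SCr)
- SAP form: (140 − age) × weight / (72 × SCr)
- Both are multiplied by 0.85 for women, which does not change the sign.

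Age 60, 60 kg, SCr 1.0 mg/dL, male:
- Protocol: (140 − 3600) / 72 = −3460 / 72 = −48.1 mL/min
- SAP: 80 × 60 / 72 = 4800 / 72 = 66.7 mL/min

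Further male examples (mL/min):

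| Age, weight, SCr | Protocol form | SAP form |
|---|---|---|
| 18, 50 kg, 0.8 | −13.2 | 105.9 |
| 65, 70 kg, 1.0 | −61.2 | 72.9 |
| 70, 70 kg, 1.2 | −55.1 | 56.7 |
| 80, 45 kg, 1.2 | −40.0 | 31.3 |

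The protocol form is negative whenever age × weight exceeds 140. At age 18 that means any weight above 140 / 18 = 7.8 kg, and at 65 any weight above 140 / 65 = 2.2 kg. Over a grid of ages 18 to 100, weights 25 to 200 kg and SCr 0.3 to 5.0 mg/dL, the largest value is −0.86. No adult gets a positive result.

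**2. The renal item.** Three passages matter when set side by side:

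- Table 12 ranks measured above calculated CrCl and leaves eGFR as an alternative. It does not ask for the same method over time. The echocardiography/MUGA row of the same table does ask for one modality per patient.
- SAP 5.6.4 calls for change and shift tables and gives no rule on renal method.
- SAP 7.1 chooses the baseline by closeness to first dose and, for ties, by latest database entry. Neither step looks at method.

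Mixing is therefore permitted, though not prescribed. The documents give no data on how far measured and calculated CrCl differ, so the size of the artefact cannot be computed.

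**3. The renal DLT.** Table 12 prefers a measured value, while Table 7 names the calculated one. Calculated CrCl can be obtained whether or not a measured value exists, so a site can follow both. What is missing is a sentence saying that the preference stops short of the DLT.

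**4. Weight at every visit.** Protocol Tables 1 and 2 schedule chemistry at some visits without a weight: Cycle 1 Days 8 and 15 and Cycle 2 Day 8 in Phase 1, and Cycle 1 Day 8 in Part C. A per-visit derivation needs a stated rule for which weight to use there.

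**5. Proteinuria.** The protocol trigger names one dipstick grade and the SAP names a range. SAP Section 6 states that its analyses agree with the protocol, and on this item the wording does not.

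**The case against.** The best case on the other side has four parts.

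- **The bracket may not be in the source.** The equations were read from text extracted from a PDF, where a bracket in a fraction can shift. This stands as a reason to check the PDF. The same closing position in both protocol equations, against the other position throughout the SAP, makes a chance shift less likely but does not exclude it.
- **No one would act on a negative CrCl.** Criterion 9f names a standard formula and does not point to Table 12, nor does Table 7. This largely stands. A reader might infer that patients would be wrongly excluded or counted as DLTs. The documents do not support that, because an impossible value exposes itself and the formula is identified by name.
- **The SAP summarizes by parameter and never says to pool the three measures.** Other data-handling rules sit in a sponsor document that SAP 7.4 cites and that is not available here. This stands too: mixing is a possibility left open, not an instruction.
- **The protocol's proteinuria wording does not exclude higher grades.** The SAP makes its quantitative summary conditional on such data being collected, and no endpoint, entry criterion or DLT uses it. A reader might infer that the heaviest proteinuria will go unquantified. The text does not establish that. It shows only that the two triggers differ.

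**Conclusion.** The bracket, as printed, is wrong for every adult and disagrees with the SAP. It should be corrected, subject to confirmation in the source PDF. Its practical effect on entry and DLT decisions is probably small.

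The renal-item point holds in a limited form: the change-from-baseline and shift tables can mix methods because nothing prevents it. A reader might go further and infer that eGFR could carry a patient across the 50 or 30 mL/min cut-off. It could not under these rules. Criterion 9f accepts calculated or measured CrCl, Table 7 accepts calculated CrCl, and neither names eGFR. Nor do Tables 12 and 7 truly collide on the DLT, since Table 7 already says which value counts. They need one clarifying sentence.

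The proteinuria difference is a mismatch between protocol and SAP, not a wrong value.

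The sign result needs no assumption beyond adult age and weight. The individual values rest on the example patients. The renal-item conclusion assumes that the unseen data-handling document has no same-method rule.

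**What to change.** 1. Check the equation in the source PDF. If the bracket is as described, print the numerator in protocol Table 12 as (140 − age) × weight, as the SAP does, for both sexes.
2. In SAP 5.6.4, derive Cockcroft-Gault CrCl at baseline and at every chemistry visit, and base the change and shift tables on it. State which weight applies where none is scheduled, for example the most recent recorded one. List measured CrCl and eGFR as separate parameters. Carry the same rule into the analysis plan for Part C.
3. Add to Table 12 that its preference for a measured value does not apply to the renal DLT, which Table 7 defines on calculated CrCl.
4. Reconcile the proteinuria trigger between protocol Table 12 and SAP Table 8.

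The cost is a few lines in each document and one programmed derivation. Age, weight and creatinine are already collected, so items 1 to 3 need no new procedure. Whether item 4 changes site practice depends on how the sponsor reconciles the two triggers.

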7.1.1. Efficacy Assessments

Efficacy assessments (including CT scan/MRI) will be performed by Investigator/local radiologist according to RECIST v1.1 guidelines at the timepoints outlined in the Schedule of Events (Section 1.3).

Radiological assessment must include MRI/CT of the chest, abdomen (and pelvis, if clinically indicated or obtained at baseline) at each time point, as well as assessment of all other known sites of disease. MRI of the brain should be performed if signs or symptoms suggestive of CNS metastases are present. The same method of assessment and the same technique must be used to characterize each identified and reported lesion at screening, throughout the study including the follow-up period. Contrast-enhanced CT scans or MRIs are the preferred methods for tumor assessments. If a contrast agent is contraindicated in a patient, obtain a non-contrast chest CT and enhanced MRI of the abdomen (and pelvis if clinically indicated). A CT should be performed using a ≤ 5 mm contiguous reconstruction algorithm.

For Part B and C of this study, all radiological imaging will be performed as indicated in the Site Imaging Manual provided by the central imaging core laboratory. Scans will be submitted to a Sponsor designated central imaging core laboratory for response assessment including RECIST v1.1, and/or exploratory analysis (eg, volumetric and viable tumor measurements). Detailed information regarding submission of images to the central imaging core laboratory is found in the Site Imaging Manual.

Note that complete response and partial response (PR) require confirmatory CT or MRI repeat assessment at least 4 weeks after the first detection of response. PET may be used to upgrade a response to a CR in a manner similar to a biopsy in cases where a residual radiographic abnormality is thought to represent fibrosis or scarring.²⁸

Patients who discontinue without documented radiographic disease progression per RECIST 1.1 should continue to undergo tumor assessments/scans according to the Schedule of Events until radiographic PD per RECIST v1.1 is documented, the study is completed, or consent is withdrawn.

7.1.2. 12-Lead Electrocardiogram

Electrocardiograms (ECGs) will be collected using a 12-lead tracing. Patients should be in supine position in a rested and calm state for at least 10 minutes before ECG assessment is conducted. If the patient is unable to be in the supine position, the patient should be in most recumbent position as possible. ECGs should be performed on D1 of every cycle and more frequently for patients in Part A1 during the PK lead in period (for PK lead in, see Table 13). For ECGs during Extension, see Table 3.

All ECGs should be performed in triplicate on Day 1 of Cycles 1 to 3 for all patients in Parts A1, A2, B and C. Patients in Part A1 will have additional triplicate ECGs performed during selected time points of the PK Lead-in period. After C3D1, ECGs are not required to be performed in triplicate unless clinically indicated. ECGs should be run consecutively, prior to blood draws or other invasive procedures. An ECG machine with the capacity to calculate standard intervals automatically should be used. If an abnormal ECG finding at screening or baseline is considered to be clinically significant by the Investigator, it should be reported as a concurrent medical history condition. If there is a clinically significant abnormal ECG finding during the treatment period, this should be recorded on the AE eCRF, according to standard AE collection and reporting processes.

For Parts A2, B, and C, all ECGs will be performed using local ECG machines. Patients in Part A1 will have both local and central ECGs (see [Table 13](#)).

For central ECGs in Part A1 (see Schedule of Events; [Table 1](#)), the Investigator or delegate will review all ECGs for any on treatment decisions. Once signed, the original ECG tracing will be retained with the patient's source documents. All digital ECG data will be transferred electronically for central analysis of heart rate, PR, R-R, and QT intervals by an external cardiologist.

7.1.3. Cardiac Function Evaluation

The commonly available imaging modalities (ECHO 2D, MUGA) will be used for the evaluation of LVEF evolvement during therapy with TAS3351 to detect presence of cardiotoxicity defined by the European Society of Cardiology as a decrease in LVEF of >10% points to a value below 50%.²⁹ Imaging will be performed by the cardiologist or qualified delegate per the Schedule of Activities ([Table 1](#)). Additional on-study evaluation may be performed as needed based on physician judgment and/or symptoms or signs of LV dysfunction. Each evaluation will encompass:

- LVEF assessment using MUGA, conventional 2DE biplane Simpson method or 3DE, if available
- Clinical symptoms of Congestive Heart Failure (CHF) will be noted and graded according to NYHA

Signs of CHF will be detected by routine clinical examination, including auscultation to detect S3 gallop, tachycardia, or both.

